The risk of DKA must be considered in the event of non-specific symptoms such as nausea, vomiting, anorexia, abdominal pain, excessive thirst, difficulty breathing, confusion, unusual fatigue or sleepiness. In addition it needs to be taken into account that, due to the insulin independent mode of action, there is a possibility that ketoacidosis in patients treated with SGLT2 inhibitors is not accompanied by typical hyperglycemia as usually expected for DKA.

Patients who may be at higher risk of DKA while taking SGLT2 inhibitors include patients on a very low carbohydrate diet (as the combination may further increase ketone body production), severely dehydrated patients, and patients with a history of ketoacidosis or who are known to have a low beta-cell function reserve.

As with all drugs, the potential for hypersensitivity and allergic reactions must be taken into consideration when empagliflozin is administered. Other risks to the patients are the risks inherent to any clinical trial such as unexpected adverse clinical or laboratory events.

Although rare, a potential for drug-induced liver injury (DILI) is under constant surveillance by sponsors and regulators. Therefore, this study requires timely detection, evaluation, and follow-up of laboratory alterations of selected liver laboratory parameters to ensure patients safety.

Proprietary confidential information.

© 2016 Boehringer Ingelheim International GmbH or one or more of its affiliated companies. All rights reserved.

This document may not - in full or in part - be passed on, reproduced, published or otherwise used without prior written permission.

There are no adequate and well-controlled studies of empagliflozin in pregnant women. Empagliflozin is category C for pregnancy. Therefore, women who are of child-bearing potential will be included in this study provided that they are using adequate contraceptive methods.

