14. Bariatric surgery within the past two years and other gastrointestinal surgeries that induce chronic malabsorption.
15. Medical history of cancer (except for basal cell carcinoma) and/or treatment for cancer within the last 5 years.
16. Blood dyscrasias or any disorders causing hemolysis or unstable Red Blood Cells (e.g. malaria, babesiosis, haemolytic anaemia, thalassemia, sickle cell anaemia (sickle cell trait is allowed)).
17. Medical history and signs and symptoms of diabetic autonomic neuropathy.
18. Treatment with anti-obesity drugs 3 months prior to randomisation (i.e. surgery, aggressive diet regimen, etc.) leading to unstable body weight.
19. Current treatment with systemic steroids at time of informed consent or change in dosage of thyroid hormones within 6 weeks prior to informed consent or any other uncontrolled endocrine disorder except T2DM in the opinion of the investigator.
20. Pre-menopausal women (last menstruation ≤ 1 year prior to informed consent) who:
 - are nursing or pregnant or
 - are of child-bearing potential and are not practicing an acceptable method of birth control, or do not plan to continue using this method throughout the study and do not agree to submit to periodic pregnancy testing during participation in the trial. Acceptable methods of birth control include tubal ligation, transdermal patch, intra uterine devices/systems (IUDs/IUSs), oral, implantable or injectable contraceptives, complete sexual abstinence (if acceptable by local authorities), double barrier method and vasectomised partner.
21. Alcohol, drug or confectionary liquorice abuse within the 3 months prior to informed consent that would interfere with trial participation or any ongoing condition leading to a decreased compliance to study procedures or study drug intake in the investigator's opinion.

Proprietary confidential information.

© 2016 Boehringer Ingelheim International GmbH or one or more of its affiliated companies. All rights reserved.

This document may not - in full or in part - be passed on, reproduced, published or otherwise used without prior written permission.

22. Intake of an investigational drug in another trial within 30 days prior to intake of study medication in this trial; or participating in another trial (involving an investigational drug and/or follow-up) after discontinuing medication in that trial.

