3.3.4 Removal of patients from therapy or assessments

3.3.4.1 Removal of individual patients

An individual patient is to be withdrawn from the trial if:

- The patient withdraws consent, without the need to justify the decision.
- If a patient becomes pregnant during the trial. The patient will be followed up until birth or otherwise termination of the pregnancy.

Treatment with study drugs should be discontinued if:

- The patient needs to take concomitant drugs that interfere with the investigational product or other study medications(s).
- The patient is no longer able to participate for other medical reasons (e.g. surgery, AEs, or other diseases).
- Introduction of rescue therapy due to hyperglycemia, high HbA1c or hypertension as described in [Section 4.2.1](#) does not lead to sufficient treatment efficacy (rescue criteria still met). In this case, the reason for study drug discontinuation will be classified as "lack of efficacy".
- Occurrence of hypoglycemia (e.g. repeated hypoglycaemic episodes) or DKA that may put the patient at risk with continued participation. Patients should be assessed for ketoacidosis immediately if symptoms occur, regardless of blood glucose level. Discontinuation or temporary interruption of study medication should be considered, until the situation is clarified.

Patients who discontinue treatment prematurely will be followed up until the end of the study (for further details please see [Sections 6.2.2](#) and [6.2.3](#)).

A patient can be discontinued after discussion between sponsor and investigator if eligibility criteria are being violated, or if the patient fails to comply with the protocol (e.g. non-attendance at study assessments).

Patients who drop out during the screening phase prior to randomisation (Visit 3) will be considered screening failures. They have to be recorded as screening failure in eCRFs and no further follow-up is required.

Patients who discontinue from treatment or withdraw from the study after randomisation (Visit 3) will be considered as "early discontinuations" and the reason for premature discontinuation must be recorded in the eCRFs. The data will be included in the trial database

Proprietary confidential information.

© 2016 Boehringer Ingelheim International GmbH or one or more of its affiliated companies. All rights reserved.

This document may not - in full or in part - be passed on, reproduced, published or otherwise used without prior written permission.

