4.2.2.2 Restrictions on diet and life style

At the beginning of the Run-in period, patients will receive diet and exercise counselling by a diet specialist or trained staff member. The counselling will be based on local diet recommendations and should include a food log/intake booklet. The patients will be reminded to follow the agreed diet and exercise plan at every visit. A food intake booklet will be provided as a tool but site specific tools could also be used. Record of the actual food intake over a time of three consecutive days before the clinic visit is requested at regular intervals as indicated in the [Flow chart](#). The food intake booklet will remain with the patient and no data will be transferred to the eCRF. The respective procedure for illiterate patients (if included) is described in [Appendix 10.1](#).

Women of child-bearing potential must continue to practice an acceptable method of birth control (in accordance with the trial exclusion criteria Section 3.3.3) throughout the duration of the study.

Patients should also not take an investigational drug in another trial within 30 days prior to intake of study medication in this trial.

There are no other restrictions on diet and lifestyle.

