6.2.1 Screening and run-in period

Visit 1 (Screening)

- The screening visit is the only visit in this study that does not need to be done fasting.
- No trial procedures should be done unless the patient has consented to taking part in the trial. Patient identification numbers are available in the RDC system. If a patient is re-screened, a new patient identification number should be assigned.
- Once they have consented, the patient is considered to be enrolled in the trial and to have started screening. The patient should be recorded on the enrolment log and registered in the IRT system as a screened patient.
- BP should always be measured before any blood samples are taken. For details regarding the correct method for measuring BP, please see [Appendix 10.3](#).
- Once Visit 1 procedures are complete and laboratory results are received, inclusion/exclusion criteria must be reviewed. If the patient meets inclusion/exclusion criteria, the patient should be contacted to schedule next visit. If the patient does not meet

Proprietary confidential information.

© 2016 Boehringer Ingelheim International GmbH or one or more of its affiliated companies. All rights reserved.

This document may not - in full or in part - be passed on, reproduced, published or otherwise used without prior written permission.

inclusion/exclusion criteria the patient must be recorded in CRFs and registered in the IRT system as a Screen failure.

Visit 2.1 (Run-in period)

- From this visit onwards, patients should be fasting (no food or drinks, water only for at least 10 hours) prior to each visit.
- Inclusion/exclusion criteria must be reviewed at this visit
- BP should always be measured before any blood samples are taken. For details regarding the correct method for measuring BP, please see [Appendix 10.3](#).
- Collection of urine and blood for laboratory testing must be performed prior to administration of study medication.
- Provide patient with diet and exercise counseling. Patients should be given a food log to be completed for three consecutive days prior to Visit 3 as indicated in the [Flow Chart](#).
- Provide HBGM equipment/supplies and instruct patient on the correct use of HBGM.

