6.2.2 Treatment period

The treatment period is from Visit 3 to Visit 7.2. Patients will be dispensed medication at Visits 3, 4, and 5.2. Patients will receive a new kit number through the IRT system on each occasion. Assessments should be performed as mentioned in the [Flow Chart](#) and the respective protocol sections.

Throughout the treatment period, BP should always be measured before any blood samples are taken. For details regarding the correct method for measuring BP, please see [Appendix 10.3](#).

Visit 3 (Randomisation visit)

- Inclusion/exclusion criteria must be reviewed prior to randomization
- BP measurement and orthostatic blood pressure test should always be done before taking any blood sample.
- Collection of urine and blood for laboratory testing must be performed prior to administration of study medication.
- Collect returned run-in medication.
- Collect blood sample for PG evaluation after obtaining separate informed consent. PG sample should be collected for randomised patients only.
- Patients should be reminded about the importance of following the agreed diet and exercise plan. Patients should be given a food log to be completed for three consecutive days prior to Visit 4 as indicated in the Flow Chart.
- Provide HBGM equipment/supplies and instruct patient on the correct use of HBGM.

Proprietary confidential information.

- Instruct patient to perform a HBGM once weekly during the treatment period (more frequently if required by local authorities) in the fasted state and at any time the patient is symptomatic, i.e., experiences signs/symptoms of hyper or hypoglycemia. Instruct patient to contact site immediately if blood glucose reaches the limit described in [Section 4.2.1.](#)
- Once all visit procedures are conducted, contact the IRT system to randomise the patient and obtain medication kit numbers and dispense the medication to the patient.
- Administration first dose of study medication.
- Instruct patients NOT to take study medication on the morning of the next trial visit.

Visit 4

- BP should always be measured before taking any blood samples.
- Collection of urine and blood for laboratory testing must be performed prior to administration of study medication at each visit.
- Collect returned medication.
- New medication kit must be dispensed according to the [Flow Chart](#), and the IRT system must be contacted to obtain medication kit numbers to be dispensed.

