	A3.09	Renal insufficiency or renal impairment (assessed by eGFR)	Exclusion criterion checked	E13 + data check for any issues ¹	PPS

Table 6.2: 1 List of important protocol violations (cont.)

PV Category/ Code		Description	(Comments)	Criterion to check for PV	Exclusion from
	A3.10	Treatment with protocol excluded systemic steroids or recent change in thyroid hormone dose	Exclusion criterion checked or current treatment with systemic steroids at time of informed consent or change in dosage of thyroid hormones within 6 weeks prior to informed consent or any other uncontrolled endocrine disorder except T2DM. (Treatment with local and inhaled steroids is allowed)	E19 (protocol version 2), E20 (protocol version 1)	PPS
	A3.11	Intake of an investigational drug within 30 days prior to intake of study medication in this trial	Exclusion criterion checked (Medical judgment), depending on the type of drug given in the prior trial (only if investigational drug interferes with glucose metabolism).	E22 (protocol version 2), E23 (protocol version 1)	PPS Final decision at DBL meeting
	A3.12	Specific exclusion criterion for premenopausal women violated	Exclusion criterion checked	E20 (protocol version 2), E21 (protocol version 1)	None

Table 6.2: 1 List of important protocol violations (cont.)

PV Category/ Code		Description	(Comments)	Criterion to check for PV	Exclusion from
	A3.13	Relevant alcohol or drug abuse and other conditions affecting study compliance	Exclusion criterion checked	E21 (protocol version 2), E22 (protocol version 1)	None
	A3.14	Any other clinical condition unsafe for participation that would jeopardise patient safety while participating in this clinical trial	Exclusion criterion checked	E23 (protocol version 2), E24 (protocol version 1)	None
	A3.17	Diagnosis of autoimmune diabetes	As defined in protocol	E7	None
B	Informed consent				
	B1	Informed consent not available	Date of informed consent missing or No signature on patient's "Declaration of Informed Consent". Patient's data will not be used at all.	I8 ¹ data check or manual	All
	B2	Informed consent too late	Date of informed consent not obtained prior to any study related procedure. Minimum requirement \leq date of Visit 1/date of any study procedure	I8 ¹ data check or manual	None
C	Trial medication and randomisation				
C1	Incorrect trial medication taken				

Table 6.2: 1 List of important protocol violations (cont.)

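### Exclusion criterion 20 joins its last two grounds with *and*, so read literally it does not exclude a woman who plans to stop contraception but accepts pregnancy tests

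*Protocol*

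**What the plan says.** Protocol 3.3.3, criterion 20, concerns pre-menopausal women. Besides those who are nursing or pregnant, it excludes women who "are of child-bearing potential and are not practicing an acceptable method of birth control", and then, after an *or*, those who "do not plan to continue using this method throughout the study and do not agree to submit to periodic pregnancy testing". A list of acceptable methods follows.

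Other parts of the plan bear on the same rule:

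- Protocol 4.2.2.2 says of women of child-bearing potential that they "must continue to practice an acceptable method of birth control (in accordance with the trial exclusion criteria Section 3.3.3) throughout the duration of the study".
- Protocol 2.3 notes the lack of adequate studies in pregnancy and concludes that "women who are of child-bearing potential will be included in this study provided that they are using adequate contraceptive methods".
- Protocol 6.2.1 says of Visit 2.1: "Inclusion/exclusion criteria must be reviewed at this visit". Protocol 6.2.2 says of Visit 3: "Inclusion/exclusion criteria must be reviewed prior to randomization".
- Protocol 3.3.4.1 requires withdrawal of a patient who becomes pregnant. Discontinuation is only a possibility, after discussion between sponsor and investigator, if eligibility criteria are violated "or if the patient fails to comply with the protocol".
- SAP Table 6.2: 1, code A3.12, "Specific exclusion criterion for premenopausal women violated", is triggered when the exclusion criterion is ticked. It removes a patient from no analysis set.

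No entry shown in the amendment log changes criterion 20.

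**The concern.** The second bullet of criterion 20 has three conditions: not using contraception now, not planning to continue it, and not agreeing to pregnancy tests. A safety exclusion of this kind should make each a ground on its own. With *and* between the last two, agreeing to be tested cancels a stated plan to stop contraception.

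What is at stake is patient safety at entry. Protocol 2.3 makes contraception the condition on which women of child-bearing potential are admitted. A stated plan to stop should be caught when eligibility is reviewed. The main remaining safeguards act later: discretionary discontinuation, scheduled tests, and withdrawal once pregnant. Nothing in the efficacy analysis depends on the point.

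**Working it through.** This is a question of logic, and the plan gives no figure to reproduce. Take a woman of child-bearing potential who is neither pregnant nor nursing, and define three facts about her:

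- P: she practises an acceptable method now (criterion 20, first condition)
- C: she plans to continue it throughout the study (second condition)
- T: she agrees to periodic pregnancy tests (third condition)

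The sentence can be bracketed literally in two ways, and the evident intention gives a third rule:

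- Reading 1: excluded if not P, or (not C and not T)
- Reading 2: excluded if (not P or not C), and not T
- Three separate grounds: excluded if not P, or not C, or not T

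| P | C | T | Reading 1 | Reading 2 | Three grounds |
|---|---|---|---|---|---|
| yes | yes | yes | not excluded | not excluded | not excluded |
| yes | yes | no | not excluded | not excluded | excluded |
| **yes** | **no** | **yes** | **not excluded** | **not excluded** | **excluded** |
| yes | no | no | excluded | excluded | excluded |
| no | yes | yes | excluded | not excluded | excluded |
| no | yes | no | excluded | excluded | excluded |
| no | no | yes | excluded | not excluded | excluded |
| no | no | no | excluded | excluded | excluded |
| | | **Total excluded** | **5 of 8** | **3 of 8** | **7 of 8** |

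The row in bold is the case at issue. Both literal readings leave her eligible, so the gap does not depend on the bracketing. The row for a woman who continues contraception but refuses tests shows the same fault.

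Two of the eight rows are artificial: a woman with no method in use cannot plan to continue it. Merging the P = no rows over C leaves 2 + 4 = 6 states. Three grounds then exclude 5. Reading 1 excludes 2 + 1 = 3. Reading 2 excludes 1 + 1 = 2. The bold row is unchanged.

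Next, compare this with the rest of the protocol. Section 4.2.2.2 requires contraception throughout, makes no exception for women who accept tests, and cites 3.3.3 as its basis. That is good evidence that *or* was intended, and it is inconsistent with the literal criterion. With Section 2.3 the tension is one of purpose only, since a woman using a method at entry satisfies its words.

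**The case against.** The best defence is that the protocol already shows how criterion 20 is to be understood. Section 4.2.2.2 points back to 3.3.3 when it imposes continued contraception. An investigator who reads both has little room to enrol a woman who says she will stop. A run of negatives like this one is also often read in ordinary English as a list of separate grounds, and a site that does so applies the rule correctly. This stands, and it is why the matter is small. It does not change the text that sites are told to review at Visits 2.1 and 3.

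Other entry criteria might catch the case. Criterion 21 covers conditions that reduce compliance and criterion 23 covers conditions that endanger the patient, each in the investigator's opinion. Neither clearly covers a stated intention about contraception.

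Scheduled urine tests are a real safeguard, and the woman at issue has accepted them. A missed test is itself an important protocol violation (SAP Table 6.2: 1, code I2.02). Testing limits exposure but detects pregnancy rather than preventing it. In the flow chart as it reads in the available copy, no test is marked between Week 12 and about Week 23 to 24; the visit between is by telephone.

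Counts of logical states say nothing about numbers of patients. That is right, and they are used here only to locate the error.

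Finally, the protocol is dated 18 July 2016 and the SAP was revised on 24 March 2017. The documents do not show whether recruitment was still open or a further amendment planned, so the remedy assumes there is an occasion to make it.

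**Conclusion.** The concern holds. As written, criterion 20 does not exclude a woman of child-bearing potential who uses contraception at screening, plans to stop it and accepts testing, although Section 4.2.2.2 requires the opposite. It is a drafting error rather than a decision by the sponsor.

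The size is small. The fault shows only if the sentence is taken as literal logic, and the number of women it could admit cannot be estimated from the documents. Sample size, power, type I error, analysis sets and estimates are untouched. It deserves correction because it sits in an operative safety rule and the correction is trivial. The conclusion rests on the current wording of 3.3.3 and on the assumption, supported by 4.2.2.2, that continued contraception was meant to be a condition of entry.

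**What to change.** At the next amendment, replace the final *and* in the quoted sentence of criterion 20 with *or*. Better still, list three grounds, each sufficient on its own to exclude a woman of child-bearing potential:

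1. she is not using an acceptable method of contraception;
2. she does not intend to keep using it for the whole study;
3. she does not agree to periodic pregnancy testing.

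This also closes the gap for a woman who refuses testing.

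The edit does not need an amendment of its own. Amendment 2 made a one-word clerical correction to criterion 22 in the same list, so there is a precedent. The cost is at most a few more screen failures. The SAP can stay as it is, because code A3.12 excludes from no analysis set. The corrected wording would also make that code more reliable: a site reading the present text literally would not tick the criterion, so no violation would be recorded by that route.

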3.3.4 Removal of patients from therapy or assessments

3.3.4.1 Removal of individual patients

An individual patient is to be withdrawn from the trial if:

- The patient withdraws consent, without the need to justify the decision.
- If a patient becomes pregnant during the trial. The patient will be followed up until birth or otherwise termination of the pregnancy.

Treatment with study drugs should be discontinued if:

- The patient needs to take concomitant drugs that interfere with the investigational product or other study medications(s).
- The patient is no longer able to participate for other medical reasons (e.g. surgery, AEs, or other diseases).
- Introduction of rescue therapy due to hyperglycemia, high HbA1c or hypertension as described in [Section 4.2.1](#) does not lead to sufficient treatment efficacy (rescue criteria still met). In this case, the reason for study drug discontinuation will be classified as "lack of efficacy".
- Occurrence of hypoglycemia (e.g. repeated hypoglycaemic episodes) or DKA that may put the patient at risk with continued participation. Patients should be assessed for ketoacidosis immediately if symptoms occur, regardless of blood glucose level. Discontinuation or temporary interruption of study medication should be considered, until the situation is clarified.

Patients who discontinue treatment prematurely will be followed up until the end of the study (for further details please see [Sections 6.2.2](#) and [6.2.3](#)).

A patient can be discontinued after discussion between sponsor and investigator if eligibility criteria are being violated, or if the patient fails to comply with the protocol (e.g. non-attendance at study assessments).

Patients who drop out during the screening phase prior to randomisation (Visit 3) will be considered screening failures. They have to be recorded as screening failure in eCRFs and no further follow-up is required.

Patients who discontinue from treatment or withdraw from the study after randomisation (Visit 3) will be considered as "early discontinuations" and the reason for premature discontinuation must be recorded in the eCRFs. The data will be included in the trial database

Proprietary confidential information.

© 2016 Boehringer Ingelheim International GmbH or one or more of its affiliated companies. All rights reserved.

This document may not - in full or in part - be passed on, reproduced, published or otherwise used without prior written permission.

and will be reported. If determined by investigator as necessary for patient safety, new antidiabetic medication regimen can be started immediately after discontinuation and must be recorded in eCRFs.

For the analysis of this trial it is absolutely crucial that all planned assessments are done as planned, even if patients discontinue trial treatment. All patients who discontinue from treatment after randomisation (Visit 3 and beyond) and who do not withdraw consent will be followed up for the intended regular treatment period. All assessments related to the primary and secondary endpoints must be performed as if the patient would have remained on treatment. Details of procedures to be followed for patients prematurely terminating the trial treatment can be found in Section 6.2.3).

If a patient withdraws consent, participation in the study will end, the study medication will be stopped and the study staff will try to arrange tests for end of treatment procedures and a follow-up visit (Visit 8 procedures) with the patient for the patient's safety (For further details please see Section 6.2.3). All used medication kit boxes and remaining study medication should be returned. Patients who withdraw consent will not be contacted any more about the study.

Patients who withdraw or discontinue from the trial after randomisation will not be replaced.

